5.10. PARTICIPANT SPECIMEN COLLECTION PROCESS

Upon receipt of the DBS HIV/HCV testing kit, the participant will be required to enter the validation code that they received via SMS or email when they registered on the website on the space allocated on the test card included in the kit. If the individual is completing the DBS test with assistance from a trained worker, clinician or peer worker, a validation code is not required. Instead, the trained worker will enter the DBS kit code and their own contact details for third point of validation. Those using paper-based forms will note the unique identifier issued to each kit will enter this on their paper forms. This will ensure that the bio-specimens received are from the person who registered online. The validation code will then be verified at the laboratory to ensure there is a match with the patient information recorded online.

The participant will collect their own blood specimen according to the instructions included with the DBS HIV/HCV testing kit. The kit packaging is designed to be discreet and practical. The instructions contain advice and diagrams to guide the participant through the sample collection process step by step.

During Phase 2, some participants may be assisted by health care workers or peers to complete the specimen collection process. Training will be provided to staff and peers at the phase 2 sites, to ensure that they comply with infection control procedures.

5.11. VENEPUNCTURE SUBSTUDY

At selected clinics, participants will be asked to provide a paired sample of blood (5ml) collected via venepuncture by a healthcare professional. This will be optional for participants. Up to 1300 participants will be enrolled in the venepuncture sub study. Participants can take part in the DBS HIV and HCV study without providing this sample. The primary objective of this sub-study is to compare the analytical performance of DBS as a sample type for the diagnosis of hepatitis C (antibody and RNA) to standard of care (venous-collected samples). All samples will be tested at NSW Health Pathology laboratories. Results delivery will be as per standard of care by NSW Health Pathology to the service ordering the tests. Participants will not receive HCV treatment as part of this study. Participants that are RNA positive will be linked to standard of care to assess for HCV treatment eligibility. Reactive DBS hepatitis C results will not need a confirmatory test as the sample will be paired to a venous sample tested as per standard of care. See Appendix D.

5.12. LABORATORY TESTING PROCEDURES

Once the package is received at the NSW State Reference Laboratory for HIV, the sample will be processed then tested. HIV testing will use one of the Abbott Alinity i automated anaylser, HIV antigen/antibody combo assay. HCV testing will use the Hologic Panther, Aptima HCV Quant Dx assay which is an in vitro nucleic acid amplification test (NAAT) performed on automated platforms. All DBS samples received by the laboratory will be tested according to a specific algorithm described below and in Appendix B (see Appendix B for the testing flowchart).

The HIV 4th generation EIA has a sensitivity of >99%, a specificity of >99% and window period of 15-21 days (26). Samples found reactive by EIA will have a Western Blot test conducted consistent with routine practices. Trial data suggests the Aptima HCV NAAT has a specificity of 98.6%, and is highly sensitive (27).

All commercially available laboratory tests for HIV are not intended for use with DBS samples. HIV testing is highly regulated in Australia by the TGA and application of in-vitro diagnostic devices with alternate sample types not supported by the manufacturer involves using the product 'off-label' under the Therapeutic Goods Administration's Clinical Trial Notification (CTN) Scheme.

Testing will be done frequently to ensure a fast turn-around time for receipt of results. The NSW State Reference Laboratory for HIV has successfully participated in an established external quality assurance scheme (EQAS) for HIV testing in Dried Blood Spot samples coordinated by the US Centers for Disease Control (CDC) for more than 20 years. It is anticipated that DBS samples received by the testing laboratory will be tested and results made available within one week. This would include confirmation of HIV reactive samples by HIV Western blot. The advantage of testing of samples in a reference laboratory allows for a variety of supplemental tests to be applied in the confirmation of true test positivity. This testing may also include TGA approved nucleic acid tests for HIV for which manufacturers have made claims to support the use of DBS sample types.

DBS sample collection for HIV and HCV as an alternative to conventional venepuncture has been used for 28 years in the Needle Syringe Program surveillance system among people who inject drugs throughout Australia and has been used successfully in a growing program of early infant HIV diagnostic testing targeting resource limited and remote settings (28). Laboratory testing strategies have been successfully developed and applied for detection of HIV antigens and antibodies plus hepatitis C RNA in DBS samples. In the context of early infant diagnosis, the detection of nucleic acid (HIV pro-viral DNA) indicates HIV infection of the infant, however the detection of HIV antibodies may be due to the presence of maternal HIV antibodies in the infant sample (28,29).

5.13. RESULT PROVISION

All results will be provided via the Sexual Health Infolink (SHIL), which has an established service for providing results of HIV and sexually transmissible infections to individuals and linking the person to local care. The *Sexual Health Infolink Operations Manual 2023* outlines the responsibilities of SHIL in providing test results (29). The provision of results for the DBS study will be integrated with current operating procedures at SHIL.

Negative results will be sent to the participants via text message or email by SHIL using the following standard script: "Hi, your DBS test result is negative (ok). Stay Safe and Test often. Call [name] for more info" and "Hi, Your test result is negative (ok). Test often. Call [name] (open weekdays 9am to 5:30pm) for more information. Regards, (Nurse) NSW Sexual Health Infolink" If a

participant calls SHIL back, the DBS Results Management Business Rule outlines how SHIL staff are to proceed.

With respect to participants who return a negative result and do not have contact details (due to lack of access to a working phone, email address or stable home address) the following process will apply: sites delivering negative results will make a record of the result in the patient file and ensure mechanisms are in place to alert staff should the individual subsequently return to the service so that the result can be given.

Participants who return an invalid test result will be sent a text message or email using the following script: "Hi, please call [name] for your DBS test results (weekdays, 9-5). (Nurse).

Participants who return a test result detecting HIV or HCV will be sent a text message or email using the following script: "Hi, Please call me on [name] (open weekdays 9am to 5.00pm) for your DBS test results. Regards, (Nurse) Clinical Nurse – NSW Sexual Health Infolink.

A trained clinical nurse specialist from SHIL will speak to participants about having a confirmatory venous HIV or Hepatitis C test done and will provide advice about where participants can go for testing, such as local public sexual health clinics, GPs, or relevant clinicians in the HIV Support Program run by the Ministry of Health where appropriate. Where SHIL is delivering results on behalf of a registered site, nurses will ask the client for permission to provide this result to the associated site for assistance in engaging the client in confirmatory testing, treatment and ongoing care. Procedures for referral and booking of participants for follow-up care are outlined in the DBS Results Management Business Rule. As part of this pilot, SHIL will routinely follow-up all participants (or the relevant site) with a detectable HIV result one week after notification to ensure they have attended testing, been linked to care and offer further referrals if required.

All participants who return a detectable HIV result will be actively contacted on 5 attempts, as per recommended guidelines in the DBS results management Business Rule. If contact remains unsuccessful, the Project Coordinator and clinical governance lead at Sydney Sexual Health Centre will be alerted for follow-up.

During Phase 2, a setting/site may request to provide results directly to participants. In this situation, SHIL will provide results to a clinician at the site. The site will then provide the results to the participants. In the case of a suspected new positive HIV result, SHIL will follow up with the site to ensure that results have been provided and linkage to care has been supported. Information on participants' treatment initiation will be collected from sites via a standardised case report form. For new HIV cases, sites will confirmatory follow up venous test results (HIV), CD4 results (HIV) and information on linkage to care and treatment initiation to SHIL or the DBS Study Coordinator, and SHIL will ensure all confirmatory results are forwarded to the NSW State Reference Laboratory for HIV (St Vincent's Hospital Sydney). A specific consent process has been developed for participants to consent to site delivery of results. (Approved in amendment 6 application).

See Appendix C for the test results flowchart.

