7. EVALUATION OUTCOMES AND DEFINITIONS

The key study outcomes and their definitions are listed below

- 1. **Return rate:** proportion of DBS samples which were returned for testing. This will also be disaggregated by target population.
- 2. **HIV test positivity rate:** The numerator for calculating HIV positivity is the number of laboratory confirmed HIV positive individuals with Western Blot testing. The denominator is the number of individual 4^{thd} generation EIA tests performed during the pilot period.
- 3. **HCV test positivity rate:** The numerator for calculating HCV positivity is the number of laboratory confirmed HCV positive individuals with RNA testing on the Hologic Panther analyser. The denominator is the number of individual HCV RNA tests performed during the pilot period.
- 4. **Proportion of participants who are infrequent testers:** The proportion of DBS participants who reported at the first registration they had never tested for HIV before or had tested over 2 years

ago. This outcome measure will also be disaggregated by target population and test combination (HIV only compared to HIV/HCV dual testing).

- 5. Linkage to care rate: proportion of DBS participants who return an HIV detected test result and are reviewed by a referral clinician within 2 weeks of diagnosis. Linkage to care will be verified by the registered nurse making the follow-up call to newly diagnosed participants one week after notification of results, and information will be self-reported by the participant. Linkage to care will be reported separately for participants who receive a reactive HIV result, and those who receive a reactive HCV RNA test result.
- 6. **Mean CD4 count at diagnosis:** calculated in laboratory confirmed HIV positive individuals using flow cytometry
- 7. Re-testing rate: Proportion of DBS participants who had two or more DBS tests in the study period
- 8. Acceptability of DBS test process: Proportion of DBS participants who reported they found the DBS testing processed acceptable or highly acceptable
- 9. Cost per DBS test conducted: the costs to the health system of each DBS test done
- 10. **Cost per HIV infection diagnosed** by DBS test: the costs to the health system of each positive DBS test
- 11. **Cost per HCV infection diagnosed** by DBS test: the costs to the health system of each positive DBS test

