8. EVALUATION DATA SOURCES AND PROCEDURES

a. Brief online questionnaire at registration

All participants will complete an online survey at registration. The survey will cover sociodemographics and injecting drug use history.

b. Follow up call at 7 days

SHIL will follow up with phase 1 people who receive an HIV or HCV detected test result one week after receiving their results via a telephone call, as part of the standard of care that would include provision of assistance, support and linkage to care services for newly diagnosed people. Sites managing their own results will be responsible for ensuring people are linked to follow up care and treatment as necessary. SHIL will follow up people with detected results in the case that sites have elected for SHIL to manage results."

c. Follow-up evaluation processes

Consent to participate in the follow-up evaluation processes will be requested at the time of registration as per procedures used in a range of other previous studies. Follow-up information will be collected via a variety of methods, for example a cross-sectional survey of participants or semistructured interviews and will include questions about acceptability of self-sampling, testing preferences and confidence regarding the performance of self-sampled DBS HIV or HIV/HCV test. Follow-up of both registrants who have sent a DBS kit for testing and those who do not complete DBS testing will occur to better understand the factors influencing completion of DBS testing by individuals who register for the service. A formal evaluation of the pilot is planned from December 2022. Further detail regarding the follow-up of participants will be provided to relevant Human Research Ethics Committees as an additional amendment as soon as possible. Follow-up of participants will not commence until formal ethics approval has been granted for this process.

d. Cost

The evaluation objective assessing cost (costs per test and costs per HIV or HCV infection diagnosed) relates to all costs relating to staffing, delivery DBS HIV testing kits, laboratory testing and result

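### HCV linkage to care (outcome 5) cannot be measured consistently as written: it has no HCV definition, two call times, and no stated linkage return from sites that manage their own results

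*Protocol*

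**What the plan says.** HCV linkage to care is part of secondary objective 4 (section 2), and section 3.1 names the follow-up call as the source of linkage data.

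**Definition.** Section 7, outcome 5, gives the rate as the "proportion of DBS participants who return an HIV detected test result and are reviewed by a referral clinician within 2 weeks of diagnosis". Linkage is to be "verified by the registered nurse making the follow-up call to newly diagnosed participants one week after notification of results", from the participant's own account. It is also to be "reported separately for participants who receive a reactive HIV result, and those who receive a reactive HCV RNA test result".

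**Call time.** Section 5.3 (Clinical governance) puts SHIL's Phase 1 contact at one week for an HIV detected result and at one month for an HCV detected result. Section 8b, whose heading gives 7 days, says: "SHIL will follow up with phase 1 people who receive an HIV or HCV detected test result one week after receiving their results".

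**Sites that manage their own results.** Section 8b says: "Sites managing their own results will be responsible for ensuring people are linked to follow up care and treatment as necessary". It gives SHIL follow-up in Phase 2 only where the site has chosen SHIL to manage results. For sites that deliver results, section 5.13 adds three statements:
- "In the case of a suspected new positive HIV result, SHIL will follow up with the site", to check that the result was given and linkage supported.
- Information on "treatment initiation will be collected from sites via a standardised case report form", with no limit to HIV.
- "For new HIV cases, sites will confirmatory follow up venous test results (HIV), CD4 results (HIV) and information on linkage to care". A verb is missing, but the sentence goes on to send these items, with treatment initiation, to SHIL or the study coordinator.

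**The concern.** A reported proportion needs a population, an event, a time window and a data source that apply to everyone in it. For HIV the protocol supplies all four. For HCV it promises the result but leaves the population, event and window unstated, gives two times for the Phase 1 call, and states no linkage source for one group of participants.

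Two analysts could therefore report different HCV linkage rates from the same pilot, depending on the window they chose and when the call was made. The rate might also describe only Phase 1 and SHIL-managed participants without saying so. Sites can deliver their own results only in Phase 2, the phase for which sections 3.2 and 9 add 1000 kits or dual tests to reach the planned 1860 (1000/1860 = 54%). That share is context only, because the documents do not say how much of Phase 2 will run through such sites.

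**Working it through.** **1. Definition (section 7, outcome 5)**

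| Element | HIV | HCV |
|---|---|---|
| Who counts | HIV detected result | named only in the separate-reporting sentence |
| Event | review by a referral clinician | not stated for HCV |
| Window | 2 weeks from diagnosis | not stated for HCV |
| Source | nurse's call at one week | the same call by implication; one month in 5.3 |

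The HIV event and window can be read across to HCV, but the text does not say so.

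**2. Call against window**

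Inputs: a window of 14 days from diagnosis (section 7); a call 7 days after notification (sections 7 and 8b); and d, the days from diagnosis to notification. The documents do not give d, so 0 to 7 is assumed.

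- The call falls on day d + 7 after diagnosis.
- Days of the window still open at the call = max(0, 14 − (d + 7)) = max(0, 7 − d).
- d = 0 gives 7 days; d = 3 gives 4; d = 7 gives 0.

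Example: with d = 0, a participant reviewed on day 10 meets a 2-week definition but has not yet been reviewed when called on day 7. Unless the nurse calls again, linkage is undercounted. If diagnosis were dated from the later confirmatory venous test, d could be negative and the gap longer than 7 days.

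A one-month call, taken as day 28 or later after notification, falls on day d + 28 at the earliest. For any d of 0 or more that is past day 14, so no open days remain. The two stated HCV call times are therefore not interchangeable.

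The same arithmetic applies to HIV, where the one-week call and the 2-week window are both explicit.

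**3. Stated source of linkage information, by result route**

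| Route | HIV | HCV |
|---|---|---|
| Phase 1 | SHIL call at one week (5.3, 8b) | SHIL call at one month (5.3) or one week (8b) |
| Phase 2, SHIL manages results | SHIL follow-up (8b; one week in 5.13) | SHIL follow-up (8b; time only from its heading) |
| Phase 2, site manages results | SHIL checks with the site, and the site returns linkage information (5.13) | treatment initiation on the case report form (5.13); no linkage item stated |

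Five of the six combinations have a stated source. The venepuncture sub-study is left out of the table because its results go through standard of care.

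Treatment initiation partly fills the sixth. A person who started treatment was evidently reviewed, and a start date inside the window, if recorded, would show review inside it. It does not identify people reviewed but not treated, and it does not date the review.

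**The case against.** The strongest reply concerns the third part. It is an omission, and the places most likely to hold the answer cannot be read: the Appendix C results flowchart, the standardised case report form and the DBS Results Management Business Rule. The synopsis says of these same sites that SHIL keeps overarching governance and monitors follow-up, with no limit to HIV. The outcome is also descriptive and secondary, in a pilot, with no test or decision rule attached.

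Much of this stands. It narrows the third part to people reviewed but not treated and to the review date, and makes it conditional on what those papers contain. It leaves the first two parts untouched, since both are visible in the text. The synopsis sentence names no data item and no return, so it is not a stated data source.

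A reader might infer more than the documents support:
- *That nobody is responsible for linking HCV cases at these sites.* Section 8b gives that duty to the site, and section 5.3 (Overall governance) gives SHIL the linking of all individuals.
- *That no HCV follow-up data come back from them.* The case report form sentence covers treatment initiation without an HIV limit.
- *That their HCV cases will be scored as not linked, so the rate is biased low.* Nothing says how missing linkage is handled, and a protocol may leave that to the analysis plan. The undercount shown above comes from call timing only.
- *That governance at these sites needs rewriting as part of this point.* Section 5.3 gives clinical governance to the site, while section 3.3 gives overall governance to SHIL and local governance to the Local Health District. That is a separate wording matter, and settling it would supply no linkage data.

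**Conclusion.** The point holds in three parts. Outcome 5 has no definition for HCV although it must be reported for HCV. The Phase 1 HCV call has two conflicting times, and the earlier one can precede the close of a 2-week window by up to 7 days for d between 0 and 7. At sites managing their own results, the visible text states a linkage return for HIV but only treatment initiation for HCV.

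The first two parts rest on the protocol text alone, apart from the assumed range for d and the reading of a 2-week window across to HCV. The third also assumes that the unseen flowchart, form and business rule do not already collect the HCV review date.

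The number of people affected cannot be derived. Section 3.3 says the number of Phase 2 sites is unknown, and no share of self-managing sites is given. Severity is minor to moderate: the outcome is a descriptive secondary measure, but as written its HCV rate has no single meaning.

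**What to change.** - **Section 7, outcome 5.** Define HCV linkage as the proportion of participants with HCV RNA detected who are reviewed by a referral clinician within a named window that closes no later than the HCV call, for example 4 weeks from notification. State that the HCV call is at one month.
- **Section 8b, text and heading.** Set the HCV call to one month, as in section 5.3, and keep one week for HIV.
- **Section 5.13.** Extend the site's return to SHIL or the study coordinator to HCV RNA detected cases, with three items: date the result was given, date of clinician review, and treatment initiation. If the existing form or business rule already collects these, cite it instead.
- **HIV linkage.** Record the review date, or confirm linkage at or after day 14 from diagnosis, because the one-week call has the same timing problem.

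The cost is a protocol amendment with ethics review, three fields per HCV-detected participant at self-managing sites, and a review date or a later check for HIV cases. If the existing form already covers HCV, the site return costs only a citation, but the definition and call-time edits are still needed.

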5.14. STUDY PROCEDURE RISKS

DBS self-sampling for HIV and HCV testing should be used in circumstances where it can be demonstrated that the benefits to be gained from their use outweigh any potential risks.

Minimum performance requirements for point of care testing (PoCT) for HIV have been published by the Therapeutic Goods Administration and have been endorsed by NSW Ministry of Health (31), and

similar requirements for self-testing are relevant to DBS self-sampling for HIV testing, including the need for:

- Individuals to be given appropriate information, clear instructions in their preferred language on how to perform the test and support regarding the potential disadvantages of HIV and/or HCV self-sampling for testing in comparison to a laboratory test. In particular, individuals need a full understanding of test accuracy, including the window period and the need for re-testing.
- Appropriate support for individuals who have undergone or are about to undergo selfcollection for a HIV or HCV test, including online and telephone services. Referral details for existing support services, such as "healthdirect" (which provides 24 hour access), should be provided with the device, and DBS testing kits should have clear instructions for use.
- Providing reliable, accurate and accessible information on DBS self-sampling for HIV and HCV testing with the device to ensure users understand the purpose and limitations of the screening devices, as well as promoting locally available support services such as appropriate health information phone lines and websites to enable linkage to care and support services. This will include providing information in multiple languages and pictorial instructions.
- Informing users with negative test results and recent/on-going risk of the necessity to re-test frequently.
- Systems in place to support users who receive an HIV or HCV detected test result.

The standard testing algorithm for this study outlines this process (see Appendix B).

NSW Health notes that there is no evidence from other jurisdictions where home-based or selfsampling testing is approved that use of self-sampling devices will reduce a person's access to professional health care.

Other specific risks relating to the pilot program are as follows:

(i) Incorrect or mislabelled dried blood spot specimens

As a way of ensuring the veracity of the sample sent to the laboratory, the participant will receive a validation code when registering for the study online. The validation code will be cross-checked prior to testing of the DBS sample and again before test results are released to the participant. If participants have lost their validation code they may also call the Sexual Health Infolink on [name] to retrieve this upon correct identification. If the individual is completing the DBS test with assistance from a trained worker, clinician or peer worker, a validation code is not required. Instead, the trained worker will enter the DBS kit code and their own contact details for third point of validation.

(ii) Inaccurate results dependent on the window period and sensitivity and specificity of the test The patient information sheet (attachment 1) and information provided on the DBS website will provide appropriate information required for informed consent. This will include how the test performs in comparison to conventional laboratory HIV or HCV testing, the limitations of the test including the window period, and the need for repeat testing if there has been a recent risk event or illness. Results of DBS samples found to be reactive will not be provided to the participant until a validated confirmatory test such as Western Blot has been conducted. Information will be provided on the registration website directing individuals to seek clinical review for Post-Exposure Prophylaxis (PEP) if they think they have had an exposure to HIV within the previous 72 hours.

- (iii) Bleeding, discomfort and bruising can occur from a finger prick test.
- (iv) Participants may experience stress and anxiety while waiting for their DBS HIV or HCV test result

- (v) Participants may feel embarrassed answering some of the questions in the client survey regarding sexual behaviour. However, this has been minimised by using an online format, enabling people to provide the information in the comfort of their own home or other private location
- (vi) Participants may experience stress and anxiety and adverse personal relationship effects as a consequence of testing positive for HIV or HCV
- (vii) Sample may be from someone other than named participant

Risks (iv), (v), (vi) and (vii) could occur during routine clinical practice in sexual health and general practice clinics and are not unique to this study. Participants may withdraw from the study without penalty or any adverse effect. If participants are distressed, they will be able to contact SHIL to speak to a trained registered nurse who will be able to provide referral for support if required. This will be made clear to participants on the DBS website and during the online registration process. Participants who return a detected HIV or HCV result will receive intensive support and follow-up, as is standard clinical practice.

